**Hypothesis:** Our hypothesis is that using Oxytocin while the cervical ripening balloon is in place will result in more rapid labor courses, without increase morbidity or increasing the need for operative delivery.

Objective: The purpose of this study is to determine the optimal method for induction of labor in multiparous women with an unfavorable cervix.

Hypothesis: Our hypothesis is that using Oxytocin while the cervical ripening balloon is in place will result in more rapid labor courses, without increase morbidity or increasing the need for operative delivery.

Inclusion Criteria:

- Age > 18 years
- Gestational age > 34 weeks
- Prior spontaneous vaginal delivery
- Clinical or ultrasound estimated fetal weight < 4500 grams
- Singleton gestation
- Cervical dilation < 2 cm on admission

Exclusion Criteria:

- Placental abruption, chorioamnionitis, or systemic infection prior to induction
- Rupture of membranes prior to induction
- More than 1 prior cesarean delivery
- Placenta within 2 cm of cervical os
- Any contraindication to vaginal delivery
- Any contraindication to cervical ripening balloon placement or oxytocin administration

Study Protocol:

- Identify patients who are multiparous, who will be undergoing induction of labor, and obtain informed consent either during prenatal care or on admission to labor and delivery.
- Randomize patients to receive cervical ripening balloon (CRB) alone followed by oxytocin or CRB and simultaneous oxytocin for induction via random number generator in sequential opaque envelopes.
- CRB is placed digitally or with a speculum and balloon is inflated with 35 mL of normal saline. Care of the CRB per current MacDonald guidelines. Oxytocin is administered either when the balloon is removed (after 12 hours) or if spontaneously expelled sooner if in the control group, or is initiated when the balloon is placed in the experimental group.
- Fetal monitor and labor management is per current guidelines for all participants.

Statistical Analysis Plan:

Power Calculation: Using the data from Pettker, in the subgroup analysis of multiparous women, the rates of vaginal delivery within 24 hours were 75% and 55% respectively for women receiving transcervical Foley with oxytocin compared with transcervical Foley alone. Under assumption of 80% power and an alpha of 0.05, we estimated we would need 90 patients in each arm to demonstrate a 20% reduction (from 75% to 55%) in primary outcome in the treatment group.

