Data Collection: Demographic variables (maternal age, race, parity, gestational age at delivery, indication for induction), time to expulsion of CRB, cervical dilation after expulsion, time to delivery, cesarean delivery rate, operative vaginal delivery rate, perinatal complications (including postpartum hemorrhage, chorioamnionitis, or cervical laceration), neonatal outcomes (including APGAR scores)

Analysis Plan: Intention to treat analysis, calculation of RR, 95% CI. Categorical and continuous variables will be assessed using parametric and non-parametric tests where appropriate.

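### Does a 12-hour balloon removal mentioned only for the control group bias the comparison of time to expulsion?

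*Combined protocol and SAP*

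**What the plan says.** The Study Protocol section sets the start of oxytocin by arm. For control: "Oxytocin is administered either when the balloon is removed (after 12 hours) or if spontaneously expelled sooner if in the control group". For the experimental arm: "or is initiated when the balloon is placed in the experimental group". The 12-hour figure appears only in the control clause. The same bullet also says, without separating the arms: "Care of the CRB per current MacDonald guidelines". That guideline is not reproduced.

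The Data Collection paragraph lists "time to expulsion of CRB, cervical dilation after expulsion" among many items. The Analysis Plan reads "Intention to treat analysis, calculation of RR, 95% CI", followed by "Categorical and continuous variables will be assessed using parametric and non-parametric tests where appropriate". It names no test for time to expulsion. It gives no rule for a balloon that was taken out rather than expelled, and it neither names nor excludes a time-to-event method.

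**The concern.** A balloon that is removed has no expulsion time. Suppose removal after 12 hours applied to control women only, and the removal time were entered as if it were an expulsion. Control times would then stop at about 12 hours while experimental times could run on. A late experimental expulsion would rank behind a removed control balloon, whatever that control balloon would have done if left in place. Analysis by intention to treat does not prevent this, because it happens with every randomised woman kept.

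The balloon phase is where the two regimens differ, and the error would run against the hypothesis that simultaneous oxytocin "will result in more rapid labor courses, without increase morbidity or increasing the need for operative delivery". Equal arms could be reported as slower ripening with simultaneous oxytocin, and a real gain could be missed.

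**Working it through.** **The plan's own figure.** The documents give no expulsion times and no calculation for this item. The only figure to reproduce is the sample size in the Power Calculation (75% vs 55%, 80% power, alpha 0.05 taken as two-sided). With pooled variance:

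n = [1.96·√(2·0.65·0.35) + 0.842·√(0.75·0.25 + 0.55·0.45)]² / 0.20² ≈ 88.1, so 89 per arm against the stated 90.

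It agrees, and it does not depend on balloon times. It supplies only the 90 per arm used below.

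**What the text supports.**

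| Condition needed for the bias | What the documents say |
|---|---|
| Removal after 12 hours in control only | Not stated. The figure is a parenthesis in a sentence on when oxytocin starts, and removal triggers oxytocin only in the control arm, so that is where it would naturally appear. Balloon care is referred to one guideline. |
| Removal time entered as expulsion time | Not stated. The item is time to expulsion, and the control clause itself distinguishes removal from expulsion. |
| A sizeable share of balloons still in place at 12 hours | Not given. |

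**Direction if the first two conditions held.** Let q be the share not expelled by 12 hours, with identical true times in both arms. Only pairs in which both women pass 12 hours (probability q²) are affected: there the control woman is always recorded earlier instead of half the time. So

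P(control recorded earlier, ties counted half) = 0.5·(1 − q²) + q² = 0.5 + q²/2.

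This is 0.505 at q = 10%, 0.520 at 20%, 0.545 at 30% and 0.625 at 50%. The direction holds for any distribution.

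**Size if the first two conditions held.** Simulation with no true difference, 90 per arm, nobody dropped, control times cut at 12 hours. Weibull times (shape 1.5, assumed; experimental times cut at 24 hours; 3,000 to 4,000 trials per row), two-sided false-positive rate, nominal 5%:

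| Not expelled by 12 h | t-test | Mann-Whitney |
|---|---|---|
| 2.7% | 5.7% | 5.5% |
| 7.6% | 6.4% | 5.0% |
| 14% | 12.0% | 6.3% |
| 28% | 46.2% | 16.3% |
| 40% | 85.6% | 47.8% |

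Lognormal times (log-SD 0.6, assumed; experimental times uncut; 2,000 trials per row), rate of a false finding that oxytocin is slower, nominal 2.5%:

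| Not expelled by 12 h | t-test | Mann-Whitney | Log-rank, removals censored |
|---|---|---|---|
| 5% | 4.9% | 2.5% | 3.0% |
| 10% | 10.1% | 3.4% | 2.7% |
| 20% | 32.0% | 5.8% | 2.1% |
| 30% | 71.6% | 19.1% | 2.5% |
| 50% | 100% | 81.2% | 2.1% |

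With a true 20% shortening (lognormal), raising q from 5% to 30% lowers power from 56% to 6% for the t-test and from 69% to 39% for Mann-Whitney. Censored log-rank keeps 60–64% at every q. With no true effect, the difference in medians is distorted by at most 0.02 hours up to q = 30%.

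**Relaxing the conditions.**
- Same removal time in both arms (Weibull, medians 8 and 8 h): 5.0% false positives for both tests.
- The protocol says after 12 hours, not at 12 hours. Spreading control removals over 12–14 hours (assumed; medians 8 and 8 h) lowers false positives from 49% to 33% (t-test) and from 14% to 10% (Mann-Whitney).

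**Testing an obvious repair.** One could enter every balloon not spontaneously expelled, including those out early for another reason, at a common 12 hours and apply Mann-Whitney. If early exits were 10% in the experimental arm and 2% in control (assumed), with identical true times, this falsely shows the experimental arm as slower in 12%, 13% and 10% of trials at medians of 5, 6 and 8 h, against 2.5% nominal. At 5 and 6 h, Mann-Whitney with a control-only cut and no repair gives 3% and 4%.

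**The case for a change.** The strongest case for a change is that the control-only reading is a fair one. Under it the direction of error is certain, and it grows large for both tests once about 30% of balloons remain at 12 hours. Nothing in the plan rules out the biased analysis, and the choice stays open until the data are seen. Dropping the removed women would be worse: at q = 20% the t-test falsely favours control in 94% of trials and Mann-Whitney in 58%. Whether a balloon was expelled or removed may be hard to recover later if it is not recorded, and a written rule would cost one sentence and one data field.

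The mechanism and the arithmetic stand. What does not stand is the step from silence to a faulty analysis. The plan leaves the test to judgement, and times piled up at 12 hours are a poor case for a t-test, which supplies the largest figures. Censoring the removals is open to the analyst and leaves no directional bias. The expelled-or-removed distinction already determines when a control woman starts oxytocin, so site staff must make it there. Nor is one written rule clearly best: the common 12-hour rule can introduce its own bias, and with true medians of 7 and 9 h it has 52% power against 57% for log-rank.

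**Conclusion.** No change to the plan follows. The bias needs three things together that the documents do not state: removal after 12 hours in control only, removal times analysed as expulsion times, and a substantial share of balloons still in place at 12 hours. Without the first or the second there is no directional error. Without the third it is slight: with at most 10% remaining, Mann-Whitney stays close to nominal and the t-test reaches about 10% in the wrong direction against 2.5%. These sizes rest on assumed Weibull and lognormal times.

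The documents are silent on removal in the experimental arm; they do not contradict themselves, and the local guideline may answer the question. What is missing is an unwritten counting rule for one listed item, which an analyst can fill by treating both arms alike and not counting a removal as an expulsion. Vaginal delivery within 24 hours, its relative risk and the 90 per arm are unaffected.
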